## **10 EFFICACY**

The analysis of ORR will take place after all randomized subjects fall within one of the following categories:

- completed scheduled study treatment and completed at least 28 weeks on the study;

Idera Pharmaceuticals, Inc.  
 Statistical Analysis Plan  
 Protocol Number: 2125-MEL-301

- 
- prematurely discontinued study treatment and completed at least 28 weeks on the study;
  - withdrew, were lost to follow-up, or died before completing at least 28 weeks on the study.

The OS study analysis will take place when 392 deaths have occurred or approximately 36 months after the last subject is randomized, whichever occurs first. All tables, figures, and listings will be produced for the final study analysis. All efficacy tables, listings, and figures will use the ITT Analysis Set.

For determination of best overall response by RECIST v1.1, response assessments of CR and PR require confirmation by imaging  $\geq 4$  weeks after the initial documentation of CR or PR.

## **10.1 ANALYSIS OF THE PRIMARY ENDPOINT FAMILY**

### **10.1.1 Independent Reviewer-Assessed ORR by RECIST v1.1**

The final and sole analysis of ORR assessed by blinded independent review using RECIST v1.1 will test the response proportions of the two treatment arms using a stratified Cochran-Mantel-Haenszel (CMH) test for two proportions by the randomized strata as defined in [Section 9.4](#). To allow for adequate time for response and confirmation, the analysis of ORR will take place no sooner than when all randomized subjects completed scheduled study treatment and completed at least 28 weeks on the study; prematurely discontinued study treatment and completed at least 28 weeks on the study; or withdrew, were lost to follow-up, or died before completing at least 28 weeks on the study.

The generic SAS procedure call is:

```
proc freq data=<dataset name>;
  tables strata*response*treatment / cmh ;
run;
```

ORR is defined as the percentage of subjects achieving a CR or PR out of the total number of subjects included in the analysis population. The CR or PR must occur prior to PD and the start of any subsequent anticancer therapy. Subjects with not evaluable, unknown, or missing best response will be handled as non-responders; i.e., they will be included in the denominator when calculating the ORR. The independent reviewer-assessed best overall response and ORR by RECIST v1.1 with 95%, two-sided, confidence intervals (CIs) using the Wald's binomial method will be provided for each treatment arm. The percentage difference of ORR between the two treatment arms with a 95%, two-sided CI, and the p-value from the stratified CMH test will be provided. In support of ORR analysis, the

Idera Pharmaceuticals, Inc.  
Statistical Analysis Plan  
Protocol Number: 2125-MEL-301

---

summary statistics for duration of active follow-up times for all subjects will be provided (see the summary under subject disposition).

The following summary and figures will be provided:

- Independent Reviewer-Assessed Response by RECIST v1.1
- Swimmer's Plot of Independent Reviewer-Assessed Response by RECIST v1.1 for ORR Responders
- Waterfall Plot of Maximum Percent Reduction from Baseline in Individual Sum of the Longest Diameters of Target Lesions, Assessed by Independent Reviewer
- Spider Plot of Individual Percent Change from Baseline in Sum of the Longest Diameters of Target Lesions Over Time, Assessed by Independent Reviewer

The following efficacy listings will be provided:

- Independent Reviewer-Assessed Target Lesions
- Independent Reviewer-Assessed Non-Target Lesions
- Independent Reviewer-Assessed New Lesions
- Independent Reviewer-Assessed Response by RECIST v1.1
- Independent Reviewer-Assessed Response by irRECIST
- Independent Reviewer-Assessed RECIST v1.1 Tumor Response Endpoints (Best Overall Response, ORR, DCR, DRR, DoR)

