#### **4.5 DETERMINATION OF THE SAMPLE SIZE**

In this study, ORR and OS comprise a primary endpoint family; both have a priori hypotheses and will be tested for statistical significance. ORR will be tested first followed by OS. The fallback method for the primary endpoint family will be applied to control the study-wise Type I error rate. Under the fallback method,  $\alpha_1 = 0.02$  is assigned to the one-sided ORR test and an alpha of 0.005 is saved for the one-sided OS test. If the ORR test is significant at  $\alpha_1 = 0.02$ , this alpha is unused and will be passed to the OS test as an additional alpha of 0.02, giving a total alpha for the OS test of 0.025.

With 454 subjects planned with a 1:1 randomization ratio, this test will have 90% statistical power (calculated based on chi-square test) to demonstrate an increase in the ORR from the expected response of 12% for ipilimumab alone to 24% for the IMO-2125 + ipilimumab combination, at a 0.02 one-sided level of significance.

A sample size of 454 subjects also provides 90% power to test the alternative hypothesis of  $HR \leq 0.677$  at an  $\alpha$  of 0.005 (one-sided). The HR of 0.677 corresponds to an improvement in the median survival from 11.4 months (the historical control for ipilimumab alone) to 16.85 months with the IMO-2125 + ipilimumab combination. The number of required deaths to reach the 90% power is 392.

The OS power calculations are based on log-rank test and assume that the trial will have ~20 months of uniform accrual, an overall study duration up to 56 months, and a 10% drop-out rate. If a total alpha of 0.025 is available for the OS significance test under the fallback

Idera Pharmaceuticals, Inc.  
Statistical Analysis Plan  
Protocol Number: 2125-MEL-301

---

method, then this test will have 90% power to test the alternative hypothesis of  $HR \leq 0.72$  at an  $\alpha$  of 0.025 (one-sided). This corresponds to an improvement in the median survival from 11.4 months (the historical control for ipilimumab alone) to 15.8 months with the IMO-2125 + ipilimumab combination.

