## **7.2 MULTIPLE COMPARISONS AND MULTIPLICITY**

The Type I error rate will be adjusted for tests of both endpoints (ORR and OS) in the primary endpoint family. ORR will be tested first followed by OS. The fallback method for the primary endpoint family will be applied to control the study-wise Type I error rate.

Idera Pharmaceuticals, Inc.  
Statistical Analysis Plan  
Protocol Number: 2125-MEL-301

---

Under the fallback method,  $\alpha_1 = 0.02$  is assigned to the one-sided ORR test and an alpha of 0.005 is saved for the one-sided OS test.

- If the ORR test is significant at  $\alpha_1 = 0.02$ , this alpha is unused and will be passed to the OS test as an additional alpha of 0.02, giving a total alpha for the OS test of 0.025. The OS test will then be performed at the significance level of 0.025.
- If the ORR test is not significant at 0.02 level, then this alpha of 0.02 will not be available to be passed on for the OS test. The OS test will be performed at the originally reserved alpha of 0.005.

No further adjustment of the Type I error rate will occur. All analyses of secondary endpoints will be descriptive.

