### 8.2.10 Strata Used for Analysis

As stated in the protocol, the strata may be collapsed as appropriate with the goal of avoiding strata with too few subjects (the threshold for number of subjects per stratum was pre-defined as 5%). At the time of the finalization of the current version of the SAP, the distribution of subjects across randomization strata was known. The distribution was provided to the Sponsor's medical monitor for review. If a stratum had <5% of subjects, the stratification factor level was combined with another based on clinical judgment. Based on this assessment, stratification factor levels were combined as follows:

1. Metastasis stage M1c and BRAF mutation positive
2. Metastasis stage M1c and BRAF mutation wild type
3. Metastasis stage Other and BRAF mutation positive
4. Metastasis stage Other and BRAF mutation wild type

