#### **9.4 STRATIFICATION FACTORS**

The number of subjects at each stratification factor level at randomization and from the clinical data will be summarized using frequencies and percentages and listed. The summary will be by marginal levels of duration of prior anti-PD-1 therapy ( $\geq 12$  weeks vs  $< 12$  weeks), metastasis stage (M1c vs other), and BRAF mutation status and prior targeted therapy (BRAF wild type [i.e., negative], BRAF mutation positive with prior targeted therapy, or BRAF mutation positive with no prior targeted therapy) as well as the 12 stratification cells. The listing will show the randomized and clinical data stratification levels for each subject.

The duration of anti-PD-1 therapy in weeks will be calculated using start and end dates reported on the Prior Systemic Anticancer Treatment page of the eCRF as (therapy end date – therapy start date + 1)/7 when a therapy is referred to as “PD-1 inhibitor”.

Metastasis stage will be identified from the Baseline Disease Characteristics page of the eCRF as M1c or Other (if not M1c).

Idera Pharmaceuticals, Inc.  
Statistical Analysis Plan  
Protocol Number: 2125-MEL-301

---

BRAF mutation status is reported on the Baseline Disease Characteristics page of the eCRF as negative or positive. Prior targeted therapy for BRAF mutation positive subjects will be identified as the treatment category of prior systemic anticancer therapy of BRAF inhibitor, MEK inhibitor, other targeted therapy, or any combination of these therapies for those subjects with “Positive” BRAF mutation.

[Section 8.2.10](#) describes how the stratification factors are combined. The combined stratification levels will be summarized showing the levels with metastasis stage (M1c or Other) and BRAF mutation status (BRAF wild type or BRAF mutation positive).

The following summaries will be provided:

- Stratification factor levels as randomized
- Stratification factor levels derived from the clinical data
- Stratification factor levels as combined

The following listing will be provided:

- Stratification factor levels

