### 10.1.3 Analysis of OS

The analysis of OS will be performed after 392 deaths or approximately 36 months after the last subject is randomized, whichever occurs first. If the test for ORR is significant, based on the fallback method description in [Section 4.5](#), overall survival will be tested using a one-sided, stratified log-rank test with a significance level of 0.025. The same strata used in the stratified analysis of ORR will be employed in the analysis of OS. If the p-value is  $\leq 0.025$ , the null hypothesis will be rejected with the conclusion that OS in the IMO-2125 + ipilimumab combination arm is statistically superior. Otherwise, if the test for ORR is not significant, the overall survival will be tested using a one-sided, stratified log-rank test with a significance level of 0.005. If the p-value is  $\leq 0.005$ , the null hypothesis will be rejected with the conclusion that OS in the IMO-2125 + ipilimumab combination arm is statistically superior.

OS will be summarized with median, first, and third quartiles of Kaplan-Meier estimates with corresponding 95% CIs calculated by the Brookmeyer-Crowley method [[Brookmeyer, 1982](#)] with log-log transformation. Kaplan-Meier estimates and 95% CIs will also be produced at OS landmark time points at 1 and 2 years. The 95% CIs for Kaplan-Meier estimates at each of the OS landmark time points will be calculated using Greenwood's formula with log-log transformation. OS summaries will include the number of subjects at risk, the number of subjects who died, and the number of censored subjects. In addition, the survival follow-up, defined as the duration between the date of randomization and the date of last contact, in months will be analyzed by reverse Kaplan-Meier method, median and its corresponding 95% CI will be summarized. The figure will identify the number of subjects at risk at each scheduled visit and censored times on the curve. The HR and a 95% CI will be estimated using a Cox proportional hazards model, stratified by the same strata used in the analysis of ORR.

The following table and figure will be provided for OS:

- Overall Survival
- Kaplan-Meier Plot of Overall Survival

The following efficacy listing will be provided:

- Overall Survival

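### Does SAP 10.1.1 turn the planned one-sided 0.02 ORR test into a two-sided one, on conflicting strata?

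*SAP*

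**What the plan says.** The level and direction of the ORR test are set outside the section that describes its computation.

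- SAP 7.2, on multiplicity, says the 0.02 "is assigned to the one-sided ORR test and an alpha of 0.005 is saved for the one-sided OS test". Protocol 15.1 and 15.4 say the same.
- SAP 4.5 bases the ORR power on 12% versus 24% "at a 0.02 one-sided level of significance".
- SAP 4.2 states the ORR hypothesis as an increase on the combination.
- SAP 10.1.1 names a stratified CMH test, shows a generic PROC FREQ call with the CMH option, and says the difference and its two-sided interval will be given "and the p-value from the stratified CMH test will be provided". It states no threshold and no sidedness for the test.

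On strata:

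- SAP 10.1.1 refers to the randomized strata as defined in Section 9.4.
- SAP 9.4 describes summaries of the marginal levels "as well as the 12 stratification cells", then refers to 8.2.10 for how the factors are combined and names the combined levels.
- SAP 8.2.10, titled Strata Used for Analysis, says "stratification factor levels were combined as follows" and lists four strata: M1c or other, crossed with BRAF positive or wild type.
- SAP 10.1.3 adds: "The same strata used in the stratified analysis of ORR will be employed in the analysis of OS".

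**The concern.** Read alone, 10.1.1 can mislead. With two arms and a binary response, the CMH option returns a 1-df chi-square p-value, which is two-sided and carries no sign. A programmer who compared that number with 0.02 would be testing at one-sided 0.01. Taken literally, a significantly lower ORR on the combination would also pass, and would release alpha to OS. The OS section, by contrast, says one-sided and gives both cut-offs.

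The strata reference looks like a second fault. The phrase randomized strata suggests the 2 x 2 x 3 = 12 cells, whereas 8.2.10 has four and drops duration of prior anti-PD-1 therapy. OS takes the same strata, so both primary p-values would be affected.

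The stakes would be real. The ORR verdict decides the first primary endpoint and sets the OS level at 0.025 or 0.005. With 392 deaths and HR 0.72, OS power is Phi(sqrt(392)/2 x |ln 0.72| - z). With sqrt(392)/2 x |ln 0.72| = 3.252, that is Phi(3.252 - 1.960) = 90.2% at 0.025 and Phi(3.252 - 2.576), about 75%, at 0.005.

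**Working it through.** **Inputs.** 454 subjects at 1:1, so n = 227 per arm; 12% versus 24%; 0.02 one-sided; power calculated on a chi-square test (all SAP 4.5).

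**The plan's own figure.** For the pooled two-proportion test, power = Phi[(d - z x se0) / se1].

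- d = 0.24 - 0.12 = 0.12; pooled rate 0.18.
- se0 = sqrt(2 x 0.18 x 0.82 / 227) = 0.03606.
- se1 = sqrt((0.12 x 0.88 + 0.24 x 0.76) / 227) = 0.03562.
- One-sided 0.02: z = 2.054, so (0.12 - 0.0741) / 0.03562 = 1.290 and power = 90.1%.

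The stated 90% is therefore a one-sided 0.02 calculation. The same formula needs 226 per arm for 90%, against 227 planned. Exact enumeration of the uncorrected chi-square gives 90.6%.

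**The misreading.** If the undirected p-value is compared with 0.02, z = 2.326. Then (0.12 - 0.0839) / 0.03562 = 1.014 and power = 84.5% (85.2% by enumeration). With 27/227 responders on ipilimumab alone, the smallest significant count on the combination, unstratified, is 43 (difference 16/227 = 7.0 points) one-sided and 46 (19/227 = 8.4 points) under the misreading. Counts of 43 to 45 would change verdict.

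**Does the SAP ask for the misreading?** Set the sections side by side.

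| Section | Threshold | Sidedness of the test |
|---|---|---|
| 4.5 | 0.02 | one-sided |
| 7.2 | 0.02 | one-sided |
| 10.1.1 | none | none; two-sided only for intervals |

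The 84.5% takes the threshold from 7.2 and drops the sidedness stated there. Section 10.1.1 says only that a p-value will be provided and does not tie it to 0.02. Applying 7.2 to the CMH output is routine: when the difference favours the combination, the one-sided p-value is half the printed one, so the criterion is a printed p-value of at most 0.04 in that direction. The same formula at two-sided 0.04 returns 90.1%.

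**Wrong direction.** A one-sided test of an increase cannot be significant when the combination arm has the lower ORR. Even under the misreading, if treatment affects neither endpoint, the chance of any rejection is at most 0.02 + 0.005 = 0.025. For a claim of benefit the misreading is conservative: enumeration puts its upper-tail null rate at 0.0097.

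**Strata.** Following 10.1.1 to 9.4 leads on to 8.2.10 and the four combined levels. Protocol 15.4.1.2 allows collapsing and leaves the detail to the SAP. The SAP modification history for version 2.0 says subjects from small strata are combined.

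The documents give no cell counts, so size was checked by simulation with assumed independent shares: duration 80/20, stage 50/50, BRAF groups 60/25/15, and 12% versus 24% in every cell. Power at one-sided 0.02 was 90.6% with 12 strata and 90.7% with four; null rejection was 1.9% and 2.0%. In a separate simulation with blocks of four within cells, the two verdicts differed in about 0.3% to 1.3% of trials.

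**The case for a change.** The best case for an edit is that 10.1.1 describes the sole analysis of the first primary endpoint in an open-label trial, so it should be usable without reading other sections. Its code prints an undirected p-value, no sentence says how to convert it, and the OS section shows that the authors knew how to write the criterion out. The strata phrase, taken at face value, disagrees with 8.2.10, and nothing says outright whether the four strata use values as randomized or from the clinical data. Two sentences would settle it.

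The factual part stands: 10.1.1 does not restate one-sided 0.02, does not cite 8.2.10 directly, and its strata wording is loose. The inference does not.

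- The contrast with OS is thinner than it looks. Section 10.1.3 says one-sided but gives no rule for converting the log-rank statistic either. If the word is enough for OS, it is enough for ORR in 4.5 and 7.2.
- The code is labelled generic, so it is a template.
- The choices are not left until results are seen: sidedness, level and the four strata are all written in the SAP.
- The word randomized in 10.1.1 can fairly be read as choosing as-randomized values over the clinical-data values that 9.4 also tabulates.
- A 12-cell sensitivity analysis would bring back the sparse cells that 8.2.10 was written to avoid, and 10.1.2 already plans an unstratified one.

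**Conclusion.** The concern does not call for a change. The SAP specifies a one-sided ORR test at 0.02 for an increase, and followed as written it has the planned power (90.1%). The loss of 5.7 points, to 84.5%, and the release of alpha after an unfavourable ORR result both depend on ignoring the word one-sided in the section that sets the threshold. Even that error would be conservative for a claim of benefit on ORR.

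The strata wording is a clerical inconsistency that 8.2.10 and the pointer in 9.4 resolve in favour of the four strata. Its effect on power is about 0.1 point, which rests on assumed cell shares and a common treatment effect across cells. Individual verdicts would differ in roughly 1% of trials or fewer under similar assumptions. An experienced analyst would halve the p-value, check its direction and use the strata of 8.2.10, and the result is sound.

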### **10.1.2 Sensitivity Analysis of ORR**

The main analysis of ORR will be repeated for FAS and Per Protocol Analysis Set as sensitivity analysis. In addition, a sensitivity analysis using an unstratified Chi-square test for two proportions will be performed. The "best case scenario" sensitivity analysis will also be performed with the subjects who do not have any tumor response prior to discontinuation imputed as responders, versus the main ORR analysis with these subjects imputed as non-responders.

The following summaries will be provided:

- Objective Response Rate by RECIST v1.1 for FAS and Per Protocol Analysis Set
- Un-stratified and Best Case Scenario Analysis of Objective Response Rate by RECIST v1.1

Note: Un-stratified and "best case scenario" sensitivity analyses are included in the Independent Reviewer-Assessed Response by RECIST v1.1 table.

Idera Pharmaceuticals, Inc.  
Statistical Analysis Plan  
Protocol Number: 2125-MEL-301

---

### 10.1.3 Analysis of OS

The analysis of OS will be performed after 392 deaths or approximately 36 months after the last subject is randomized, whichever occurs first. If the test for ORR is significant, based on the fallback method description in [Section 4.5](#), overall survival will be tested using a one-sided, stratified log-rank test with a significance level of 0.025. The same strata used in the stratified analysis of ORR will be employed in the analysis of OS. If the p-value is  $\leq 0.025$ , the null hypothesis will be rejected with the conclusion that OS in the IMO-2125 + ipilimumab combination arm is statistically superior. Otherwise, if the test for ORR is not significant, the overall survival will be tested using a one-sided, stratified log-rank test with a significance level of 0.005. If the p-value is  $\leq 0.005$ , the null hypothesis will be rejected with the conclusion that OS in the IMO-2125 + ipilimumab combination arm is statistically superior.

OS will be summarized with median, first, and third quartiles of Kaplan-Meier estimates with corresponding 95% CIs calculated by the Brookmeyer-Crowley method [[Brookmeyer, 1982](#)] with log-log transformation. Kaplan-Meier estimates and 95% CIs will also be produced at OS landmark time points at 1 and 2 years. The 95% CIs for Kaplan-Meier estimates at each of the OS landmark time points will be calculated using Greenwood's formula with log-log transformation. OS summaries will include the number of subjects at risk, the number of subjects who died, and the number of censored subjects. In addition, the survival follow-up, defined as the duration between the date of randomization and the date of last contact, in months will be analyzed by reverse Kaplan-Meier method, median and its corresponding 95% CI will be summarized. The figure will identify the number of subjects at risk at each scheduled visit and censored times on the curve. The HR and a 95% CI will be estimated using a Cox proportional hazards model, stratified by the same strata used in the analysis of ORR.

The following table and figure will be provided for OS:

- Overall Survival
- Kaplan-Meier Plot of Overall Survival

The following efficacy listing will be provided:

- Overall Survival

### 10.1.4 Sensitivity Analysis of Overall Survival

The analysis of OS will be repeated for FAS and Per Protocol Analysis Set. In addition, sensitivity analysis of stratification effects will be performed using an HR estimator with a

Idera Pharmaceuticals, Inc.  
Statistical Analysis Plan  
Protocol Number: 2125-MEL-301

---

corresponding 95% CI that uses an un-stratified HR estimator and un-stratified log rank test for the ITT Analysis Set.

The Kaplan-Meier plot of OS will be used to assess the proportionality of hazards and to determine if there is a delayed treatment effect. If a delayed treatment effect is observed, results from a Fleming-Harrington weighted log-rank test with  $\rho = 0$  and  $\gamma = 0.5$  will be presented to test the equality of the survival curves between the treatment groups. These weights were chosen a priori anticipating the survival curves could be similar for the first 3 months. If appropriate based on the proportional hazards assessment, the restricted mean survival time will be compared between the treatment arms. These two sensitivity analyses will be conducted using the ITT Analysis Set.

The following summaries will be provided for these sensitivity analyses of OS:

- Overall Survival for FAS and Per Protocol Analysis Set
- Un-stratified Overall Survival
- Overall Survival Using Weighted Log-Rank Test
- Overall Survival Using Restricted Mean Survival Times

